At the interim analysis (20 patients/arm), the incidence of death or mechanical ventilation, grade ≥ 3 elevations in liver transaminases, or neutropenia will be estimated. We assume that the underline rate is 40%, 10%, or 24% for the three incidences in placebo group respectively, and if the rate in duvelisib group is $\geq 15\%$ higher than that in the placebo group in either of the three incidences, the trial may be stopped due to the safety concern. It also translates to stop the study if 3 or more excess events in duvelisib group are observed in either of the three incidences. Operating Characteristics, the probability of trial stopping due to ≥ 3 excess events based one simulation study, is listed in the below table.

AEs	Underline event rate in Placebo arm	Underline event rate in Duvelisib arm						
		5%	10%	20%	30%	40%	50%	60%
death or mechanical ventilation	40%	0%	0.02%	0.7%	4.8%	16.6%	37.4%	62.7%
grade ≥ 3 elevations in liver transaminases	10%	0.79%	5.7%	32.8%	65.8%	87.9%	97.2%	99.7%
neutropenia	24%	0.07%	0.6%	7.3%	26.1%	52.7%	77.3%	92.6%

In addition to the study stopping rules based an interim analysis, the Independent Data Monitoring Committee (IDMC) will review, on a monthly basis, the number of Grade 3 and/or Grade 4 adverse events in each arm, including neutropenia and elevated transaminases, and consider stopping or suspending accrual to the study if the frequencies of Grade 3 or Grade 4 adverse events are significantly higher among subjects in the duvelisib arm compared with subjects in the control arm.

Analysis of Safety Data

The primary safety endpoints include death or mechanical ventilation, grade ≥ 3 elvation in liver transminases, and neutropenia within 4 weeks. The cumulative incidence rate of each safety endpoint will be calculated with 95% confidence interval by randomized arms, and compared by Fisher's exact test.

Handing of Missing Data

For the safety endpoints and secondary endpoints, missing data will not be imputed, summaries and analyses will be based on the observed cases. For the primary efficacy analysis, every effort will be made from the informed consent form design to clinical follow up to reduce the missing data. Patients withdraw consent before the primary endpoint can be measured will be replaced.

Demographics and Baseline Characteristics

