9. Dilute cell/CryoStor mixture immediately with appropriate culture medium. This can be performed in a single step. The dilution medium should be between 20–37 °C. A dilution ratio of 1:10 (sample: medium) or greater is recommended.

10. Plate cells appropriately.

11. Culture the cells or use immediately.

Shipment:

Patient samples from secondary sites will be shipped in real-time overnight on Monday-Wednesday so that samples will be received no later than Friday. Each sample will be shipped on adequate amounts of dry ice. Emory University will cover the cost for shipment of the patient samples

APPENDIX H: Table to guide the IDMC during review of potential toxicity in the duvelisib arm at the time of the interim safety analysis

Table 1: Approximate probability of observing excess instances of mechanical ventilation or death in the duvelisib treatment arm at the time of the interim analysis.

		True Underlying Duvelisib Rate								
		20%	25%	30%	35%	40%	45%	50%	55%	60%
Approximate probability of observing $\geq X$ excess instances of mechanical ventilation or death in the duvelisib arm compared to placebo	X = 0	7.9%	15.2%	25.2%	37.2%	50.0%	62.6%	73.9%	83.2%	90.2%
	X = 1	3.9%	8.6%	15.9%	25.7%	37.3%	50.0%	62.5%	73.9%	83.4%
	X = 2	1.7%	4.4%	9.1%	16.3%	25.9%	37.4%	50.0%	62.6%	74.1%
	X = 3	0.7%	2.0%	4.8%	9.5%	16.6%	26.1%	37.5%	50.0%	62.7%
	X = 4	0.2%	0.8%	2.3%	5.1%	9.8%	16.8%	26.1%	37.4%	50.0%

Note: The true underlying placebo rate is assumed to be 40% in this table

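### The section 15.1 safety table understates the chance of 3 or more excess events at 20 per arm by up to 7.9 points, and the chance that any of the three triggers fires is not given

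*Combined protocol and SAP*

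**What the plan says.** The stopping rule for safety in section 15.1 applies at the interim look: "At the interim analysis (20 patients/arm), the incidence of death or mechanical ventilation" is estimated there, together with grade 3 or higher transaminase elevation and neutropenia. The placebo rates are assumed: "We assume that the underline rate is 40%, 10%, or 24% for the three incidences in placebo group respectively". A duvelisib rate at least 15 percentage points above placebo on any of the three means that "the trial may be stopped due to the safety concern". The plan then puts the rule on the count scale: "It also translates to stop the study if 3 or more excess events in duvelisib group are observed in either of the three incidences".

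A table follows, with one row per outcome and true duvelisib rates of 5, 10, 20, 30, 40, 50 and 60%. It is described as the probability of stopping for 3 or more "excess events based one simulation study, is listed in the below table". The simulated distribution is not stated, and the table is not called approximate.

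Appendix H gives the IDMC a second table, for death or ventilation only, with excess thresholds of 0 to 4 and a 40% placebo rate. It is titled "Approximate probability of observing excess instances of mechanical ventilation or death in the duvelisib treatment arm at the time of the interim analysis". Neither table gives the probability that at least one of the three triggers is met.

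**The concern.** The rule is about whole events, so the quantity it needs is the probability that one Binomial(20, p) count exceeds another by 3 or more. Some printed values cannot be that. The clearest sign is in Appendix H: with both arms at 40%, it gives 50.0% for an excess of 0 or more. Equal counts satisfy that condition, and two arms of 20 often tie, so the true value must be above 50%.

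The rule also fires on any of three outcomes, while the table treats each alone. The row with a 24% placebo rate has no 24% duvelisib column, so its no-difference figure is absent.

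These are the operating characteristics the IDMC holds for the interim safety review. Because a trigger permits a stop but does not require one, the committee must judge how much weight it carries. If the figures are too low, it will think false alarms rarer than they are and will also underrate how often the rule detects real harm.

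**Working it through.** **Inputs (section 15.1).** n = 20 per arm; placebo rates pC = 0.40, 0.10 and 0.24; duvelisib rates pT = 0.05 to 0.60; trigger D = X(duvelisib) − X(placebo) ≥ 3, which follows from 15% × 20 = 3.

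**Step 1: find the printed figures.** A normal approximation without continuity correction is

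P = 1 − Φ( [3 − 20(pT − pC)] / √(20[pC(1−pC) + pT(1−pT)]) ).

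- Death/ventilation, 40% vs 40%: 3/√(20 × 0.48) = 3/3.098 = 0.968, so P = 16.6%. Printed: 16.6%.
- Transaminases, 10% vs 20%: (3 − 2)/√(20 × 0.25) = 1/2.236 = 0.447, so P = 32.7%. Printed: 32.8%.

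The largest absolute difference over the 21 cells is 0.074 points. Four cells differ from the formula in the last printed digit (37.4 vs 37.47, 32.8 vs 32.74, 26.1 vs 26.03, 0.07 vs 0.076).

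**Step 2: exact values.** P(D ≥ 3) = sum of Bin(i; 20, pC) × Bin(j; 20, pT) over all pairs with j − i ≥ 3. Each cell shows printed / exact, in %:

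| Duvelisib rate | Death/ventilation (placebo 40%) | Transaminases (10%) | Neutropenia (24%) |
|---|---|---|---|
| 5% | 0 / 0.00 | 0.79 / 1.43 | 0.07 / 0.10 |
| 10% | 0.02 / 0.05 | 5.7 / 9.0 | 0.6 / 1.0 |
| 20% | 0.7 / 1.1 | 32.8 / 40.7 | 7.3 / 10.2 |
| 30% | 4.8 / 6.7 | 65.8 / 73.1 | 26.1 / 32.1 |
| 40% | 16.6 / 21.0 | 87.9 / 91.4 | 52.7 / 59.8 |
| 50% | 37.4 / 43.9 | 97.2 / 98.1 | 77.3 / 82.1 |
| 60% | 62.7 / 68.9 | 99.7 / 99.7 | 92.6 / 94.5 |

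The exact value is equal or higher in every cell. Eleven of the 21 gaps exceed 2 points; the largest is 40.73 − 32.8 = 7.93. A simulation of 400,000 pairs of counts at 40% vs 40% gave 21.1%, so simulating counts does not produce 16.6%. For neutropenia at 24% in both arms, which is not printed, the exact value is 17.6% and the uncorrected approximation gives 13.3%.

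**Step 3: Appendix H.** All 45 cells round to the same uncorrected formula, with 0 to 4 in place of 3. Exact values are higher by up to 6.8 points. At equal 40% rates the exact probability of an excess of 0 or more is 56.4%, against 50.0% printed. By symmetry, ties have probability 2 × (56.4 − 50.0) = 12.8%.

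**Step 4: any of the three triggers, no added risk.** The single probabilities are 0.2099, 0.0899 and 0.1762.

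- Independent outcomes: 1 − (0.7901 × 0.9101 × 0.8238) = 0.408.
- Any dependence: at least the largest, 21.0%; at most the sum, 47.6%.
- Assumed within-patient latent normal correlations of 0.3, 0.5, 0.7 and 0.9 (simulated): about 38.4, 36.4, 34.4 and 31.8%.

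**Step 5: the design alternative.** Death/ventilation is 40% vs 15% and there is no added toxicity. The death/ventilation trigger then has probability 0.0030.

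- Independent outcomes: 1 − (0.9970 × 0.9101 × 0.8238) = 0.252.
- Any dependence: 17.6% to 26.9%.
- The same four correlations: about 24.6, 23.7, 22.8 and 21.8%.

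**The case against.** The case for leaving this alone is that little depends on the table. The threshold comes from 15% of 20 patients and was not calibrated to these probabilities. The rule is advisory, the IDMC sees unblinded data, and Grade 3 and 4 events are also reviewed monthly by arm. The error makes the rule look less sensitive to harm than it is, so participants are no less protected than stated. Ten of the 21 cells are within 2 points, and the two printed no-difference cells are off by 4.4 and 3.3 points, not 7.9. Appendix H calls itself approximate. The plan claims no overall false-trigger rate, and any single value for one needs a correlation that the documents do not give. A simulation from a normal model could also have produced the section 15.1 values, so the word simulation may be literally true.

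Much of this stands and limits the weight of the point. How the table was made cannot be told from the document, and the any-trigger figure is an omission, not an arithmetic error. But section 15.1 carries no approximate label and describes its figures as probabilities for a rule defined on whole events, which they are not. An advisory rule also needs accurate figures, because the committee must decide how far to act on a trigger. The any-trigger bounds need no correlation assumption, and the largest no-difference figure printed in section 15.1 (16.6%) is below even the lower bound of 21.0%.

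**Conclusion.** The concern holds. The section 15.1 values are not the probability of 3 or more excess events for counts at 20 per arm. They are too low by up to 7.9 points, both where duvelisib adds no risk and where it does harm. This rests only on the plan's own rates, sample size and threshold, with independent patients. Appendix H follows the same approximation; its label is a partial defence, but its handling of ties is wrong for counts.

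With no added risk, at least one trigger fires in 21.0% to 47.6% of trials whatever the dependence; the 40.8% figure assumes independent outcomes. Even if duvelisib achieves the hoped-for reduction and adds no toxicity, the chance is 17.6% to 26.9%. The primary analysis and the trigger are unaffected. This should be fixed, but it does not undermine the design.

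**What to change.** - Recompute the section 15.1 table and Appendix H from exact binomial counts, and say in section 15.1 that this is the method.
- Add a 24% duvelisib column, so that the neutropenia row has a no-difference figure.
- Add a row for the probability that any of the three triggers fires, under (i) no difference on any outcome and (ii) 40% vs 15% on death/ventilation with no added toxicity. State the correlation assumption and show the range.
- Give the corrected figures to the IDMC before the interim review.

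The cost is recalculating two tables and adding one column and one row. No change to the trigger or sample size is needed. The stated false-alarm probabilities will look less favourable.

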1.1 Synopsis

This randomized placebo-controlled phase 2 study will evaluate whether a two-week exposure to duvelisib, a gamma/delta PI3K inhibitor, reduces inflammation in the lungs in patients with severe SARS-CoV-2 infection and COVID-19 who do not require mechanical ventilation at study initiation. The primary objective of the study is to determine the efficacy of duvelisib treatment in preventing death or the need for mechanical ventilation among patients with WHO-defined severe COVID-19. Key secondary endpoints will be reductions in oxygen requirements of patients and improvements in their performance status, safety and tolerability of duvelisib in the setting of COVID-19, biomarkers of inflammation, and generation of IgG antibody responses to SARS-CoV-2 spike protein. The study will determine if a two-week exposure to duvelisib beginning soon after presentation with severe COVID-19 warrants further evaluation in a larger clinical study.

Title:	Duvelisib Ameliorates Manifestations of Pneumonia in Established Novel Coronavirus Infection (DAMPEN-CI)
Study Description:	This randomized placebo-controlled phase 2 clinical study will evaluate whether a two-week exposure to duvelisib in subjects with severe COVID-19 is safe and well tolerated, and whether exposure to the maximally effective dose of duvelisib will safely and favorably change inflammatory bio-markers and reduce the incidence of the composite end-point of mechanical ventilation or death following the diagnosis of severe COVID-19. We hypothesize that short term exposure to duvelisib in patients with severe COVID-19 will decrease the incidence of mechanical ventilation and death compared with placebo-treated control subjects. We also hypothesize that duvelisib will decrease inflammation and improve time to resolution of symptoms.

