opportunity to stop the trial early due to futility or safety concerns. The only groups that will have access to unblinded interim data: (a) an independent data monitoring committee (IDMC); and (b) an independent statistical team whose role will be to generate the reports to be reviewed by the IDMC. The responsibility of any data-informed recommendations regarding continuing/stopping the study or modifying the study design/protocol be restricted to the IDMC.

Power Calculation

The reported incidence of death or mechanical intubation for patients with severe COVID-19 is approximately 40% (1). Local experience with COVID-19 patients at the Emory hospitals is consistent with this estimate, as 29% of all SARS-CoV-2 positive patients (n=800) are admitted to the ICU with COVID-19, and that 22% of all admitted patients are intubated, and 37% of intubated patients die in hospital. A favorable and clinically significant result from treatment with duvelisib in high-risk COVID-19 patients would be to reduce the composite incidence of death/mechanical ventilation from 40% to 15%. A sample size of 40 subjects for each treatment group will have >80% power to detect a 25% absolute reduction in the proportion of subjects who experience death or mechanical ventilation, comparing a predicted proportion of 40% death or intubation in the control arm to 15% death or intubation in the experimental arm receiving duvelisib treatment. The calculation is based on 10% type 1 error rate and two-sided Mantel-Haenszel test with one planned interim analysis when approximately 50% of sample enrolled (N=20/treatment). For

Analysis of Primary Endpoints

Analysis of the primary end-point will be based upon an intent-to-treat analysis of all subjects who are randomized to receive duvelisib/placebo. The primary endpoint is the proportion of patients who will require mechanical ventilation or experiencing death within 4-weeks (29 days) after randomization, which will be estimated with the corresponding 95% Clopper-Pearson confidence interval for the two arms separately. Fisher's Exact test will be used to test the difference between the two arms. In addition, a logistic regression will be used to estimate the odd ratio between the two arms controlling for the baseline covariates for an improved precision of the estimation (30).

Analysis of Secondary Endpoints

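### The final safety analysis compares the arms only by Fisher's exact test, with no between-arm interval, so a non-significant result would not show how large an excess of harm remains possible

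*Combined protocol and SAP*

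**What the plan says.** The study description in the Section 1.1 synopsis makes safety one of the trial's questions: the study "will evaluate whether a two-week exposure to duvelisib in subjects with severe COVID-19 is safe and well tolerated".

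The final analysis is in Section 15.1, Analysis of Safety Data. It begins "The primary safety endpoints include death or mechanical ventilation" and adds grade 3 or higher transaminase elevation and neutropenia, all within 4 weeks. The whole comparison is then one sentence: "The cumulative incidence rate of each safety endpoint will be calculated with 95% confidence interval by randomized arms, and compared by" Fisher's exact test. That paragraph gives no alpha, no interval for the difference between arms, and no statement of how a non-significant result will be read.

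Section 15.1, Stopping Rule for Safety, covers the interim look at 20 per arm. "We assume that the underline rate is 40%, 10%, or 24% for the three incidences in placebo group respectively". A duvelisib rate at least 15 points higher on any of the three may stop the trial. "It also translates to stop the study if 3 or more excess events in duvelisib group are observed". The final analysis does not return to that quantity.

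Death or ventilation is also the primary efficacy endpoint. For it, Analysis of Primary Endpoints adds a covariate-adjusted odds ratio, with no interval stated.

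**The concern.** The sample size was set for a large efficacy effect, and the same 80 patients must answer the safety question. A Fisher p-value paired with two single-arm intervals tells the reader whether a difference was detected. It does not say how large an excess is still compatible with the data. At this size the two can diverge widely, because a clinically important excess can be present and the test can still be expected to return a non-significant result.

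The trial is meant to inform whether duvelisib goes into a larger study. Those planners need the upper limit of the excess risk. For transaminases and neutropenia the plan produces no between-arm estimate at all. For death or ventilation it produces only an odds ratio on the efficacy side.

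**Working it through.** **Inputs**
- 40 per arm, 1:1 (Section 15.1, Power Calculation; Section 1.2).
- Placebo rates of 10% (transaminases), 24% (neutropenia) and 40% (death or ventilation), from the Stopping Rule for Safety.
- Excess examined: 15 points, the interim trigger.
- Alpha for the safety test: not stated, so this is an assumption. Two-sided 5% matches the 95% intervals. Two-sided 10% is the only type 1 error the plan states, and it is stated for efficacy.
- Complete data at 40 per arm. The plan gives no dropout rate, and safety data are analysed as observed. Fewer observed patients would lower power.

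**1. The plan's own figure.** "A sample size of 40 subjects for each treatment group will have >80% power to detect a 25% absolute reduction", from 40% to 15%, at two-sided 10%. The pooled rate is 0.275. Under the null, SE = sqrt(2 × 0.275 × 0.725 / 40) = 0.0998. Under the alternative, SE = sqrt((0.40 × 0.60 + 0.15 × 0.85) / 40) = 0.0959. Power = Φ((0.25 − 1.645 × 0.0998) / 0.0959) = 81.5%. The stated power reproduces as a fixed-sample normal approximation. It concerns a 25-point efficacy effect, and no power is given for safety.

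**2. Power of the final Fisher test for a 15-point excess.** Power is the sum, over all pairs (x, y) with two-sided Fisher p < alpha, of Bin(x; 40, p + 0.15) × Bin(y; 40, p). Exact enumeration gives:

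| Endpoint | Placebo vs duvelisib | Power, 5% | Missed, 5% | Power, 10% | Missed, 10% |
|---|---|---|---|---|---|
| Transaminases | 10% vs 25% | 33.4% | 66.6% | 45.0% | 55.0% |
| Neutropenia | 24% vs 39% | 22.5% | 77.5% | 33.3% | 66.7% |
| Death or ventilation | 40% vs 55% | 21.5% | 78.5% | 28.8% | 71.2% |

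Every endpoint is missed more often than not at either alpha.

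**3. What the planned output would hide.** Take 10/40 on duvelisib and 4/40 on placebo, a difference of 0.15. Fisher p = 0.14. The Wilson 95% limits are 0.142 to 0.402 and 0.040 to 0.231. Newcombe limits for the difference:
- lower = 0.15 − sqrt((0.25 − 0.142)² + (0.231 − 0.10)²) = −0.02
- upper = 0.15 + sqrt((0.402 − 0.25)² + (0.10 − 0.040)²) = +0.31

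The same observed 15-point difference at 16/40 vs 10/40 gives p = 0.23, and at 22/40 vs 16/40 gives p = 0.26.

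**4. The interim safeguard, counted separately.** With 20 per arm and a true 15-point excess, the chance of 3 or more excess events is 58.2%, 57.1% and 56.7% for the three endpoints (exact). Appendix H shows 50.0% for the 40% vs 55% case, because its entries follow an uncorrected normal approximation. If every interim flag counted as detection, both the interim rule and the final test would miss the excess in 38-42% of trials per endpoint at 5%, and in 35-41% at 10%.

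**The case against.** The plan nowhere says that a non-significant test means the drug is safe. A reader might infer such a rule from the synopsis and the Fisher sentence together, but the documents do not contain it. The point is only that the plan is silent on how non-significance will be read and supplies nothing better to read.

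A reader might also take 67-79% as the failure rate of the whole safety assessment. That is not supported either. The figure belongs to one test, per endpoint, at an assumed alpha. The interim rule, the monthly committee review of grade 3 and 4 events by arm, and the descriptive summaries in Section 16.1 all stand beside it. They guide stopping or describe events, however, and none gives a final interval for excess risk.

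Nor do the documents make 15 points a harm margin. It is an observed-difference trigger at 20 per arm, after which the trial may be stopped. Turning it into a pass/fail margin would be hard to defend, above all for death or ventilation. It would also perform poorly: with truly equal rates, the upper 95% Newcombe limit falls below 15 points in only 54%, 36% and 29% of trials at placebo rates of 10%, 24% and 40%.

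Finally, low power for toxicity is usual in an 80-patient phase 2 trial. That stands, and it is a reason to report intervals rather than rely on a test.

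**Conclusion.** The concern holds as a gap in the final safety analysis. Fisher's exact test is the only between-arm comparison planned there. Transaminases and neutropenia have no between-arm interval, and death or ventilation has only an efficacy odds ratio with none stated. A non-significant result would be more likely than not under a true 15-point excess on any of the three endpoints: 67-79% of trials at two-sided 5%, or 55-71% at 10%. This assumes 40 evaluable patients per arm and the plan's placebo rates, and it describes the final test alone. The result does not depend on which alpha was intended. It is a worthwhile correction to the analysis, not a flaw in the design.

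**What to change.** In Section 15.1, Analysis of Safety Data:
- For each of the three endpoints, make the duvelisib-minus-placebo risk difference with a 95% Newcombe interval the main comparison.
- Keep Fisher's p-value as descriptive.
- State that non-significance will not be read as absence of harm, and that the report will give the upper limit as the largest excess not excluded.

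Do not add a 15-point pass/fail margin.

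The cost is a few sentences and a little more analysis, with no new data. The downside is a more cautious safety statement. Even with equal observed counts, the upper limit would be about +14 points at 4/40 in each arm and +19 at 10/40 in each arm.
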